### 3.3.2 Supportive Care Guidelines

- Nausea/Vomiting: Treat as needed and consider initiation of prophylactic anti-emetic therapy. Please note: Ondansetron and related drugs are not recommended since they may interfere with the metabolism of sunitinib. Ondansetron may contribute to QT interval prolongation. Aprepitant, is a moderate CYP3A4 inhibitors that should be avoided if possible, or used with caution.
- Diarrhea: Manage with loperamide as needed (maximum = 16 mg per day).
- Hand-foot syndrome: Treat with topical emollients (e.g. Aquaphor), topical steroids, and/or anti-histamines. Vitamin B6 (pyridoxine 50-150 mg oral per day) may also be used.

### 3.4 QUESTIONNAIRES

The MDASI-BT will be utilized for this portion of the study. The instrument will be administered at baseline and then at the time of each evaluation that also includes imaging. Of note, the MDASI-BT will need to be given prior to informing the patients about the results of the imaging study. Full instruments are provided in the Appendix 13.3 In addition, information regarding demographics and treatment history will be collected as part of the larger study and used in this analysis.

The MDASI-BT consists of symptoms rated on an 11-point scale (0 to 10) to indicate the presence and severity of the symptom, with 0 being “not present” and 10 being “as bad as you can imagine.” Each symptom is rated at its worst in the last 24 hours. Symptoms included on the instrument include those commonly associated with cancer therapies, and those associated with the underlying disease. The questionnaire also includes ratings of how much symptoms interfered with different aspects of a patient’s life in the last 24 hours. These interference items include: general activity, mood, work (includes both work outside the home and housework), relations with other people, walking, and enjoyment of life. The interference items are also measured on 0 - 10 scales. The average time to complete the instrument is 5 minutes. The MDASI-BT has been translated into 18 languages, but the English language version will be

used for this study.[12] Non-English-speaking patients will complete the questionnaire with the assistance of an interpreter during the clinic visit.

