### 1.2.6 Rationale for The Patient-Reported Outcomes:

This study seeks to establish effective therapy for sarcomas of the CNS. We hypothesize that single agent sunitinib will result in anti-tumor activity. However, given the potential toxicity of sunitinib, it will be important to determine whether any determined anti-tumor effect is

associated with improvements in symptoms or whether a worsening of symptoms offsets the increase in survival.

Precedence for measuring “non-therapeutic” endpoints exists in oncology research. For example, Gemcitabine was approved by the FDA partially as a consequence of the decrease in pain reported in pancreatic patients who were treated, not on the basis of survival improvement which was modest, at best. There have been efforts in neuro-oncology to evaluate secondary endpoints using validated instruments as an additional indicator of benefit.

The M.D. Anderson Symptom Inventory-Brain Tumor Module (MDASI-BT) allows the self-reporting of symptom severity and interference with daily activities. The MDASI-BT has demonstrated reliability and validity in the adult primary brain tumor patient population.[12] This tool represents a modification of the widely used and validated MDASI, with particular attention to symptoms common in patients with brain tumors. The availability of validated instruments provides an opportunity to prospectively assess the impact of treatment, both positive and negative, on patients. The evaluation of symptom burden in this study will assist in finding the best possible treatment with the least toxicity.

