### **3.2 DRUG ADMINISTRATION**

Sunitinib 50 mg will be self-administered orally, once daily on an outpatient basis. Sunitinib will be administered at a dose of 50 mg daily for 2 consecutive weeks followed by 1 week of rest. Studies in patients with metastatic renal cell carcinoma, sunitinib tolerability was superior with the 2-weeks on and 1-week off compared to 4-weeks on and 2-weeks off.[\[13, 14\]](#) Patients should be instructed to store sunitinib at room temperature. Patient will take sunitinib once daily, with or without food, as desired. Patients should drink plenty of water or take rehydration fluids to avoid dehydration if diarrhea occurs. Patients should be alerted to the possibility that sunitinib capsules can cause a yellow discoloration of the skin on direct contact. If this happens, the patient should wash immediately with soap and water. Thyroid function will be monitored at baseline and at every two cycles. Dose reductions (to 37.5 mg and then 25 mg) will be permitted for patients experiencing grade 3 or 4 sunitinib-related toxicities.

**Abbreviated Title:** Ph II Sunitinib CNS Sarcomas

**Version Date:** 05-30-18

Because hypertension is a known and potentially serious but rare adverse event associated with sunitinib treatment, patients will have their blood pressure monitored and recorded at baseline and weekly during treatment including the weeks off the investigational drug either at the doctors' office or using any calibrated electronic device.

All subjects will be evaluated with magnetic resonance imaging at baseline and after every 2 cycles of treatment. Patients will continue treatment until there is disease progression or development of intolerable side effects.

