### 3.5 STUDY CALENDAR

Procedure	Screening/ Baseline	Cycle 1			Subsequent Cycles		End of treatment Visit 	Post Therapy Follow- up
		Day 1	Day 8	Day 15	Day 1	Day 15		
		+/- 3			+/- 3	+/-3		
History and PE	X	X	X		X		X	
Vital signs	X	X	X		X		X	
Performance Score (KPS)	X	X	X		X		X	X
CBC w/diff, plts	X	X	X		X		X	
Serum chemistry 	X	X	X		X		X	
Urinalysis	X							
PT/PTT INR	X							
Thyroid function tests 	X				X		X	
β-HCG (serum or urine)	X							
Blood Pressure	X	X	X	X	X	X	X	
Correlative Research Studies 		X	X		X		X	
MDASI-BT 	X						X	
Cranial MRI/CT 	X						X	
EKG/ECHO 	X							
Adverse Events 		X					→	
Concomitant Medications 	X	X			X			
Actigraphy 	X	X	X	X	X	X		
NIH Advanced	X							

*Abbreviated Title: Ph II Sunitinib CNS Sarcomas*

*Version Date: 05-30-18*

Procedure	Screening/ Baseline	Cycle 1			Subsequent Cycles		End of treatment Visit 	Post Therapy Follow- up
		Day 1	Day 8	Day 15	Day 1	Day 15		
Directives Form 								

*Total protein, albumin, calcium, phosphorus, magnesium, glucose, BUN, creatinine, sodium, potassium, alkaline phosphatase, ALT, AST, total bilirubin, direct bilirubin*

*Thyroid function tests to be done at baseline, C2D1, D1 of every other cycle and at end of treatment visit*

*Blood for correlative studies will be collected at C1D1, C1D8, C2D1 and at end of treatment visit*

*MDASI-BT to be done at baseline, at time of imaging studies throughout treatment, and at end of treatment visit*

*Response assessment to be done every other cycle within 7 days of initiation of odd numbered cycles, starting with Cycle 3 and at end of treatment visit. (Pre C1 MRI is done at screening. MRI is preferred.)*

*ECHO to be done at screening, day 1 of cycle 3 and every other cycle EKG/ECHO frequency of day 1 of the third cycle and every other cycle.*

*Adverse Event and Concomitant Medication evaluations to be documented at day 1 of each cycle and at end of treatment visit*

*ActiGraphy to be done at baseline and during cycles 1 through 6*

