### 6.3.5 Response Review

All subjects will be evaluated by cranial imaging every 6 weeks.

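### MDASI-BT forms with 24-hour recall cluster around the end of the rest week and the start of dosing, with none planned in Cycle 1 or recalling dosing days 8-13, and section 8.4 does not control for cycle day

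*Combined protocol and SAP*

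**What the plan says.** **Purpose.** Section 1.2.6 introduces the questionnaire with the words "given the potential toxicity of sunitinib, it will be important to determine". What is to be determined is whether any anti-tumor effect comes with symptom improvement, or whether worsening symptoms offset the benefit. Longitudinal evaluation of MDASI-BT severity and interference is a secondary objective (section 1.1.2).

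**Recall.** Section 3.4: "Each symptom is rated at its worst in the last 24 hours". The interference items use the same period: "The questionnaire also includes ratings of how much symptoms interfered with different aspects of a patient’s life in the last 24 hours".

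**Form schedule.** Section 3.4: "The instrument will be administered at baseline and then at the time of each evaluation that also includes imaging". Section 3.5, footnote 4: "MDASI-BT to be done at baseline, at time of imaging studies throughout treatment, and at end of treatment visit". Footnote 9 puts the end-of-treatment visit about 30 days after the last dose.

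**Scan schedule.** Section 3.5, footnote 5: "Response assessment to be done every other cycle within 7 days of initiation of odd numbered cycles, starting with Cycle 3". The footnote does not say whether the 7 days run before day 1, after it, or both.

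**Dosing.** Section 3.2: "50 mg daily for 2 consecutive weeks followed by 1 week of rest".

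**Restart conditions.** On day 1 of each cycle, section 3.3 requires no evidence of progression. It also requires non-hematological toxicity to have recovered to below grade 2, to tolerable grade 2, or to baseline.

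**Analysis.** Section 8.4 treats a form as valid if it falls within 14 days of its scheduled date and summarizes scores by time point. It does not mention the day of the cycle.

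**The concern.** With a 24-hour recall, a form describes the day before it is completed and little else. On an intermittent schedule, the choice of day decides whether the form describes a patient on drug or off drug. The 7 days before an odd cycle are exactly the rest week. The day 1 requirement of no progression also favors scanning, and so completing the form, before dosing resumes.

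Two things are at stake. First, if symptoms ease during the rest week, forms placed there give a milder picture than patients have while taking the drug. Second, if some forms fall before day 1 and others after it, a difference between two time points may reflect cycle phase rather than any real change. Both weaken the secondary patient-reported objective. Neither touches the primary endpoint or a stopping rule.

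**Working it through.** **Inputs.** Cycle of 21 days with dosing on days 1-14 (section 3.2); scans every two cycles, from Cycle 3, within 7 days of the start of the cycle (section 3.5, footnote 5); 24-hour recall (section 3.4); 14-day validity (section 8.4). Cycles are assumed to start on time.

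**The plan's own figure.** 2 cycles x 21 days = 42 days = 6 weeks. This agrees with section 6.3.5: "All subjects will be evaluated by cranial imaging every 6 weeks".

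**Basic counts.**
- Share of the cycle on drug: 14/21 = 67%.
- A form completed on day 1 before dosing comes 22 - 14 = 8 days after the last dose.
- First on-treatment form: nominal study day 42 + 1 = 43. The earliest day under footnote 5 is 43 - 7 = 36, which is Cycle 2 day 15. Even the 14-day rule reaches back only to 43 - 14 = 29, which is Cycle 2 day 8. No reading yields a form in Cycle 1.

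**On-drug recall by reading of the window.** A form day is counted as on-drug if the previous calendar day is a dosing day.

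| Reading of the window around day 1 of an odd cycle | Permitted form days | With on-drug recall | Dosing days recalled |
|---|---|---|---|
| 7 days before through day 1 | 8 | 1 (13%) | 14 |
| 3 days either side (calendar visit window) | 7 | 3 (43%) | 1-3 |
| 7 days either side | 15 | 8 (53%) | 1-7 and 14 |
| Day 1 through 7 days after | 8 | 7 (88%) | 1-7 |
| 14 days either side (section 8.4 validity) | 29 | 22 (76%) | 1-14 |

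The first four rows are readings of the schedule, and under none of them are dosing days 8-13 recalled. The last row is what the analysis would accept, and there any cycle day qualifies. These are shares of permitted days, not forecasts of when forms will be completed.

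**The other two forms.** Baseline precedes treatment (section 2.4), and the end-of-treatment form comes about 30 days after the last dose. A patient who stops before the first scan contributes only these two, both off drug.

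**Cycle day in the analysis.** The form in Appendix 13.3 has a date field and the diary in Appendix 13.2 has dose dates, so cycle day could be reconstructed. Section 8.4 does not ask for it.

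**The case against.** The case for the plan is substantial. Footnote 5 does not place the scan before day 1, so forms may fall on dosing days 1-7, and the validity rule admits forms from any cycle day. Section 1.2.6 asks about net symptom status alongside anti-tumor effect, not peak toxicity, and section 8.4 compares responders with non-responders. Pairing the form with response assessment, before the patient hears the scan result, suits that use. On-drug toxicity is also collected elsewhere: adverse events are graded by CTCAE and documented each cycle, Cycle 1 day 8 has a history and examination, and optional actigraphy covers Cycles 1-6.

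Most of this stands, and it rules out three stronger readings that a reader might infer:

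- *The form cannot show on-drug symptoms.* The permitted window includes dosing days under most readings, and symptoms that persist through the rest week would still be recorded.
- *Patients are measured after recovery.* Section 3.3 allows restart with tolerable grade 2 toxicity. Section 3.2 says only that this schedule was better tolerated than 4 weeks on and 2 off.
- *The objective is answered in the drug's favor by a calculable amount.* The adverse event rates in section 11.2.2 (fatigue 49.0%, for example) show that toxicity patients could report is common. They are not the share of patients symptomatic on a given day, and nothing in the documents says how far scores fall off drug.

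What the objection does not remove: the MDASI-BT is the only self-reported symptom scale in the trial. No planned form covers Cycle 1 or most of the second dosing week. The latitude that lets some forms fall on drug is the same latitude that leaves cycle phase uncontrolled.

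**Conclusion.** The concern holds as a weakness of timing and analysis. The schedule is poorly placed to show symptom burden on drug, and section 8.4 allows on-drug and off-drug ratings to be pooled at one time point.

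The gap itself is firm: nothing in Cycle 1 and no recall of dosing days 8-13 under any reading of the scan window. How much on-drug recall there is elsewhere depends on wording the protocol leaves open.

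Understatement of on-drug burden is probable, not shown. It rests on the assumption that symptoms ease at least partly during the rest week, which the documents do not quantify. The count also assumes cycles start on time. A cycle delayed for toxicity would move a form that follows footnote 5 later as well, so patients with more toxicity could be rated after a longer time off drug.

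This is a worthwhile, low-cost improvement to a secondary, mainly descriptive objective.

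**What to change.** These changes concern measurement and analysis only; no dosing or clinical rule is affected.

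1. In sections 3.4 and 3.5, add the MDASI-BT at the existing Cycle 1 day 8 visit. Completed on day 8, it recalls dosing day 7.
2. State that the scan-linked form is completed before dosing on day 1 of the odd cycle.
3. Record the cycle day and the date of the last dose on every form.
4. In section 8.4, replace the 14-day validity window with one that cannot cross between the rest week and the dosing weeks. For the scan-linked form, 6 days before day 1 through day 1 before dosing gives 7 form days, all recalling rest days 15-21.
5. In section 8.4, report on-drug and rest-week scores separately.

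Day 8 alone still leaves the second dosing week uncovered. A form on day 14 or 15 of the even cycle before each scan would recall dosing day 13 or 14. It is desirable but optional: day 15 carries only blood pressure and actigraphy in the calendar, and the documents do not provide for remote completion.

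The cost of items 1-5 is one extra 5-minute form at a visit that already takes place, slightly more analysis, and some forms classed as invalid under the narrower window.

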### 3.5 STUDY CALENDAR

Procedure	Screening/ Baseline	Cycle 1			Subsequent Cycles		End of treatment Visit 	Post Therapy Follow- up
		Day 1	Day 8	Day 15	Day 1	Day 15		
		+/- 3			+/- 3	+/-3		
History and PE	X	X	X		X		X	
Vital signs	X	X	X		X		X	
Performance Score (KPS)	X	X	X		X		X	X
CBC w/diff, plts	X	X	X		X		X	
Serum chemistry 	X	X	X		X		X	
Urinalysis	X							
PT/PTT INR	X							
Thyroid function tests 	X				X		X	
β-HCG (serum or urine)	X							
Blood Pressure	X	X	X	X	X	X	X	
Correlative Research Studies 		X	X		X		X	
MDASI-BT 	X						X	
Cranial MRI/CT 	X						X	
EKG/ECHO 	X							
Adverse Events 		X					→	
Concomitant Medications 	X	X			X			
Actigraphy 	X	X	X	X	X	X		
NIH Advanced	X							

*Abbreviated Title: Ph II Sunitinib CNS Sarcomas*

*Version Date: 05-30-18*

Procedure	Screening/ Baseline	Cycle 1			Subsequent Cycles		End of treatment Visit 	Post Therapy Follow- up
		Day 1	Day 8	Day 15	Day 1	Day 15		
Directives Form 								

*Total protein, albumin, calcium, phosphorus, magnesium, glucose, BUN, creatinine, sodium, potassium, alkaline phosphatase, ALT, AST, total bilirubin, direct bilirubin*

*Thyroid function tests to be done at baseline, C2D1, D1 of every other cycle and at end of treatment visit*

*Blood for correlative studies will be collected at C1D1, C1D8, C2D1 and at end of treatment visit*

*MDASI-BT to be done at baseline, at time of imaging studies throughout treatment, and at end of treatment visit*

*Response assessment to be done every other cycle within 7 days of initiation of odd numbered cycles, starting with Cycle 3 and at end of treatment visit. (Pre C1 MRI is done at screening. MRI is preferred.)*

*ECHO to be done at screening, day 1 of cycle 3 and every other cycle EKG/ECHO frequency of day 1 of the third cycle and every other cycle.*

*Adverse Event and Concomitant Medication evaluations to be documented at day 1 of each cycle and at end of treatment visit*

*ActiGraphy to be done at baseline and during cycles 1 through 6*

*End of treatment visit will occur approximately 30 days after the last dose of study drug. If the patient cannot return to the Clinical Center for this visit, a request will be made to collect required clinical labs from a local physician or laboratory. If this is not possible, patients may be assessed by telephone for symptoms.*

*As indicated in section 10.5, all subjects  $\geq$  age 18 will be offered the opportunity to complete an NIH advanced directives form. This should be done preferably at baseline but can be done at any time during the study as long as the capacity to do so is retained. The completion of the form is strongly recommended, but is not required.*

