### 2.2 SCREENING EVALUATION

Documentation / confirmation of tumor diagnosis by the NCI Laboratory of Pathology is required prior to enrollment. Slides from the most recent pre-registration biopsy or resection must be submitted for review if the previous surgery was not performed at NIH.

Within 28 days prior to registration, the following assessments are required:

1. A complete history and neurological examination (to include documentation of the patient's Karnofsky Performance Status).
2. Vital signs, blood pressure
3. Neuro-imaging confirming tumor progression shall be performed on all patients. MRI is preferred over CT scan.
4. 12-lead ECG
5. Laboratory Evaluation:
  - a. CBC with differential, platelets, PT, PTT, INR
  - b. Total protein, albumin, calcium, phosphorus, magnesium, glucose, BUN, creatinine, sodium, potassium, alkaline phosphatase, ALT, AST, total bilirubin, direct bilirubin)
  - c. Urine or serum  $\beta$ -HCG
6. Echocardiogram
7. Assessment of concomitant medications and treatments.

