### 2.3 REGISTRATION PROCEDURES

Authorized staff must register an eligible candidate with NCI Central Registration Office (CRO) within 24 hours of signing consent. A registration Eligibility Checklist from the web site (<http://home.ccr.cancer.gov/intra/eligibility/welcome.htm>) must be completed and sent via encrypted email to: NCI Central Registration Office [[contact]](mailto:[contact]).

After confirmation of eligibility at Central Registration Office, CRO staff will call pharmacy to advise them of the acceptance of the patient on the protocol prior to the release of any investigational agents. Verification of Registration will be forwarded electronically via e-mail to the research team. A recorder is available during non-working hours.

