### 2.4 BASELINE EVALUATION

All baseline evaluation procedures should be done prior to the study treatments. They do not need to be repeated if performed within 28 days prior to study drug initiation.

- A complete history and physical [including baseline blood pressure measurement and determination of Karnofsky Performance Score (KPS)] examination.
- A baseline standard NOB Gd-DPTA enhanced MRI should be performed.
- Thyroid Function Tests (and subsequently every 2 cycles)
- Urinalysis
- MDASI-BT
- Correlative Studies Blood Collection

The MDASI-BT will be completed only by the patient, unless changes in vision or weakness make this difficult. If this occurs, then the caregiver or research assistant may read the questions to the patient or assist with marking the severity number or score as described by the patient. A caregiver may complete the questionnaires as a patient proxy if the patient's deficits preclude self-report; however, this must be done at every assessment from baseline to end of treatment. Non-English-speaking patients will complete the questionnaire with the assistance of an interpreter during the clinic visit.

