### 3.3 DOSE MODIFICATIONS

Dose reductions (to 37.5 mg and then 25 mg) will be permitted for patients experiencing grade 3 or 4 sunitinib-related toxicities. If treatment is delayed for more than 4 weeks due to treatment associated toxicity, the patient will be discontinued from treatment and followed until disease progression.

- Patients may continue to receive therapy provided the following criteria are met on day 1 of each cycle:
  - ANC  $\geq 1.0 \times 10^9/L$
  - Platelets  $\geq 75 \times 10^9/L$
  - Non-hematological toxicity recovered to < grade 2 (or tolerable grade 2 or baseline)
  - No evidence of progressive disease
- With development of adverse events possibly related to sunitinib, dose reduction is permitted (see guideline below). If an adverse event is not covered by the guideline, dose may be reduced or held at the discretion of the investigator for the subject's safety. Subjects with adverse events that are manageable with supportive therapy may not require dose reductions (e.g. nausea/vomiting may be treated with antiemetics, diarrhea may be treated with loperamide, and electrolyte abnormalities may be corrected with supplements rather than by dose reduction).
- If a patient takes 75% or more of scheduled doses during a cycle, missed doses will not be reported as deviations. If the study team instructs a patient to hold the investigational drug, it will not be considered a protocol deviation.
- Increase in BP has been reported with use of anti-VEGF agents. Guidelines for management [15] is provided in Appendix 13.5

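### Pregnancy testing is scheduled once, at screening, with no test at first dose or during open-ended treatment

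*Combined protocol and SAP*

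**What the plan says.** The pregnancy test appears in two places. Section 2.2 lists a urine or serum β-HCG (item 5c) among assessments governed by the rule "Within 28 days prior to registration, the following assessments are required". The Study Calendar in 3.5 has a row beginning "β-HCG (serum or urine", marked only under Screening/Baseline.

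Three other parts of the plan could have carried the test but do not:

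- Section 2.4, the list tied to the start of dosing ("They do not need to be repeated if performed within 28 days prior to study drug initiation"), does not include β-HCG.
- Section 3.3 says "Patients may continue to receive therapy provided the following criteria are met on day 1 of each cycle". The criteria are neutrophils, platelets, recovery of non-hematological toxicity and absence of progression.
- The evaluations in 3.6 for the safety visit about 30 days after the last dose do not include β-HCG.

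On duration, 3.2 states "Patients will continue treatment until there is disease progression or development of intolerable side effects". Criterion 2.1.2.5 excludes pregnant women, 2.1.1.8 requires contraception and asks a woman who suspects pregnancy to tell her physician at once, 3.6.1 lists a positive pregnancy test as a reason for removal, and 7.3.2 treats exposure during pregnancy as a serious adverse event for reporting.

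**The concern.** The plan treats pregnancy as a serious hazard of the drug, but schedules no test after screening that could reveal one. A conception between screening and first dose, or during treatment, would be found only if the patient or a clinician suspected it and a test was then ordered. A pregnancy not yet suspected could be exposed cycle after cycle.

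Reliance on suspicion is weaker than usual here. Section 11.2.2 reports fatigue in 49.0%, nausea in 42.7% and vomiting in 33.9% of patients with solid tumors given sunitinib, so early symptoms of pregnancy could reasonably be put down to the drug. Section 2.4 also anticipates that some patients' deficits will preclude self-report on the symptom questionnaire.

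**Working it through.** There is no planned figure to reproduce. The check has two parts: reading the schedule, and working out how old the only scheduled test becomes.

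**Is the single mark deliberate?** Neighbouring calendar rows, such as blood count and chemistry, keep their marks in later columns, so the blank cells do not look like lost text. The imaging, symptom-questionnaire and EKG/ECHO rows have no marks in the treatment-cycle columns, but footnotes 4 to 6 supply on-treatment time points. The thyroid row has both marks and a footnote: "Thyroid function tests to be done at baseline, C2D1, D1 of every other cycle and at end of treatment visit". The β-HCG row has no footnote, and 2.2 agrees with the calendar. Scheduled tests therefore number one at Screening/Baseline and none at Cycle 1 Day 1, in later cycles or at end of treatment.

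**Which 28 days?** The calendar merges screening and baseline in one column, so the 28-days-before-dosing rule in 2.4 may plausibly be meant to cover β-HCG. That is the favourable reading. Read literally, 2.2 limits only the time before registration. Section 2.3 ties registration to consent ("Authorized staff must register an eligible candidate with NCI Central Registration Office (CRO) within 24 hours of signing consent"), and no maximum interval from registration to first dose is stated.

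**Inputs**

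- Oldest acceptable test at first dose, favourable reading: 28 days (2.4).
- Cycle length: 21 days (Précis and 3.2).
- Longest toxicity delay that still permits continuation: 28 days, from 3.3: "If treatment is delayed for more than 4 weeks due to treatment associated toxicity, the patient will be discontinued from treatment".
- Registration-to-dose gap g: not in the documents; assumed 0 to 14 days for the literal reading.

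**Formula.** Test age at day 1 of cycle k = 28 + g + 21 × (k − 1) + any delay. Visit windows are ignored.

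| Case | C1D1 | C2D1 | C3D1 |
|---|---|---|---|
| Favourable reading (g = 0), no delay | 28 | 28 + 21 = 49 | 28 + 42 = 70 |
| g = 0, one 28-day delay before cycle 2 | 28 | 49 + 28 = 77 | 70 + 28 = 98 |
| Literal reading, g = 14 (assumed), no delay | 42 | 63 | 84 |

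The age has no upper limit, because treatment is open-ended and no later test resets it.

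**With testing on each actual day 1.** Test age at the first dose of every cycle is 0 days. The interval between tests is nominally 21 days, or 21 + 28 = 49 after one full delay. The ±3 day visit windows can add up to 6 days, giving 27 and 55.

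**The case against.** The strongest reply is that this concerns monitoring intensity and is not a contradiction. Section 3.6.1 lists reasons for discontinuation to be documented; it does not promise surveillance, and a test prompted by suspicion could trigger removal. Safeguards do exist: a screening test, the exclusion, mandatory contraception, history and examination on Day 1 and Day 8 of cycle 1 and on day 1 of later cycles, weekly team discussion of each patient, the duty to report, and the investigator's discretion to withdraw a patient for safety. Nothing in the documents sets a re-test frequency. Section 1.2.1 notes that gliosarcoma, which makes up two of the three cohorts, is more common in men. The test ages are calendar arithmetic and do not measure harm, and the 77- and 98-day figures include a period off drug.

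Much of this is fair. The removal criterion is workable through a for-cause test, testing every cycle is a judgement based on when visits occur, and the literal-reading figures rest on an assumed gap. But none of the safeguards requires a test. Even on the favourable reading, a 28-day-old result is enough to start dosing and nothing scheduled follows it.

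**Conclusion.** The concern holds as a patient-safety gap that should be corrected. The protocol requires one pregnancy test, which may be 28 days old at first dose on the favourable reading and older on the literal one. With no delays it is 49 days old at Cycle 2 Day 1 and 70 at Cycle 3 Day 1, and there is no later limit. These figures assume a test at the edge of the 28-day window. The number of women of child-bearing potential is not given, so no exposure risk can be estimated. Objective response rate, sample size and the design's operating characteristics are not affected.

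**What to change.** For women of child-bearing potential only:

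1. Add β-HCG to the baseline list in 2.4.
2. Mark it in 3.5 at Cycle 1 Day 1, with a negative result required before dosing.
3. Mark it on the actual day 1 of each later cycle, and add a negative result to the day-1 criteria in 3.3, so that the test moves with a delayed cycle.

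Urine, or the blood already drawn on those days for blood count and chemistry, would serve. A test at the end-of-treatment visit is a sensible optional addition, since a pregnancy starting in the last cycle would otherwise still be missed by the schedule.

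As an editorial alignment, 10.3 should carry contraception through study participation, as 2.1.1.8 does, and not stop at study treatment. That reaches the visit about 30 days after the last dose for patients who stay on study; it guarantees no post-dose interval for those who withdraw (3.6.2).

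The core cost is one line in 2.4, one in 3.3, calendar marks in 3.5 and one word in 10.3. In practice it means a few extra tests, in this subgroup only, at visits already scheduled; the optional end-of-treatment test would add one more calendar mark.
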